#### **9.3.2.1.1 EXPERT REVIEW OF TTS CASES IDENTIFIED IN AUTOMATED DATA**

Review of clinical records in hospital charts for potential cases of TTS by research team clinicians will be requested as per access and approval by hospitals in PHARMO, VID, and ARS Toscana. In SIDIAP, additional review can be requested from the general practitioners

(GPs), who have access to the discharge letters. In CPRD, and for any potential cases of TTS in other data sources where hospitals do not grant access for record review, patient profile review will be performed. The electronic patient profile is a cumulative chronologically ordered record of all available electronic linkable information. This record will be reviewed by members of each local research team who are blinded to vaccination status, wherever possible.

It is anticipated that reviewers will be physicians and other life science professionals who will apply a standardised case definition of TTS (to be finalised). Data sought will include platelet counts, evidence documenting the thrombus and location, evidence of recent heparin exposure, and any evidence that a specific alternative diagnosis to TTS (eg, thrombotic thrombocytopenic purpura) accounted for the clinical presentation.

### 9.3.2.2 Thrombocytopenia With Bleeding

As of June 2021, there appears to be no standard case definition to study thrombocytopenia with bleeding following vaccination. The approach proposed to identify this outcome in automated data will follow the same approach used for TTS (Section 9.3.2.1), using bleeding instead of TE to anchor the search. It will use the same look-back period to define “new” diagnoses (Figure 5). Briefly, the working case definition for thrombocytopenia with bleeding for this study requires 2 components:

- A new qualifying bleeding event (defined below) AND
- A new diagnosis of TCP (or laboratory evidence of the same, where available) that is made from 10 days before and up to 10 days after that event

Bleeding events will include new diagnoses of clinically significant bleeds in the central nervous system, respiratory tract, gastrointestinal tract, or genitourinary tract, where “clinically significant” means requiring hospitalisation or emergency department care. Both bleeding and TCP will be ascertained using codes for diagnoses, procedures, and treatments in electronic data that are also under development within the studies conducted under the VAC4EU framework. However, as for TTS, definitions and risk window definitions may evolve during the course of the study as more knowledge is gathered about individual AESIs and while definitions are under development within the studies conducted under the VAC4EU framework.

In the primary analysis, the risk window for thrombocytopenia with bleeding extends from 1 to 42 days after vaccination (or the corresponding index date for the unexposed comparator subject). A sensitivity analyses will also evaluate the alternative risk windows of 1 to 28 days, following Pottegård et al (2021). As feasible, cases of TCP with bleeding identified from automated data will be reviewed using the approach outlined for TTS (Section 9.3.2.1.1). Information will be sought about the magnitude of thrombocytopenia (ie, platelet count) and any specific cause of the TCP.

### 9.3.3 Covariates

Covariates will be defined at the index date. Covariates will be used to define and describe the study cohorts and population of special interest, their baseline characteristics, and/or to control for confounding. Covariates proposed to define the study population and cohorts are listed in [Appendix C, Annex Table 1](#). Covariates proposed to define subgroups of interest are listed in [Appendix C, Annex Table 2](#). Covariates proposed to define baseline characteristics and to be considered in PS estimation appear in [Appendix C, Annex Table 3](#). A final list of covariates, including time-varying covariates, and their operational definitions will be specified in the SAP.

The look-back observation period to define covariates of interest will be all available information before the index date in each data source, except when an alternative look-back window is specified.

Sociodemographic characteristics and lifestyle factors will be described based on the information closest to the index date as available in each data source. Among the sociodemographic characteristics, age, sex, month/year at the index date, and geographic region are available in all data sources. Race/ethnicity is only available in the CPRD for the majority of subjects. In VID, only nationality is captured, while in ARS Toscana no information on race/ethnicity is available. Socioeconomic status information is available in all data sources. Healthcare or essential worker status is partially available in the CPRD and is fully available in ARS Toscana. However, in VID, only employment status is available. Residence in a long-term facility or nursing home is available in the CPRD, VID, and SIDIAP. Smoking status is available in a high percentage of subjects in the CPRD and in SIDIAP and is defined as partially complete in VID and PHARMO. Use of smoking cessation drugs is available in the 5 data sources. Body mass index (BMI) is only available in the CPRD and is partially available in SIDIAP and PHARMO. Obesity diagnosis and obesity surgery are available in all data sources. History of alcohol abuse is available in the CPRD. Alcohol-related disorders diagnosis codes are available in all data sources. Missing information on these variables will be described.

Medical conditions will be defined based on diagnoses (and medications and/or procedures when applicable) as recorded in the respective data sources included in the study (see [Section 9.4](#)) at any time before or on the index date, unless otherwise specified. Absence of a diagnosis code or proxies for a condition will be regarded as absence of the condition.

[figure not shown]
Use of medications at baseline will be defined based on prescriptions or dispensing as recorded in each data source ([Section 9.4](#)) in the 183 days before or on the index date, unless otherwise specified. Absence of any prescription or dispensing for a medication will be regarded as absence of the medication use at baseline. Note that some variables may not be available in all data sources, may be under recorded, or may be available only for a subset of

the study population. [Figure 6](#) shows the ascertainment windows for covariates in this study, according to their intended use.

The data source-specific definitions of the extraction algorithms of the covariates will be guided and informed through available algorithms from VAC4EU COVID-19 vaccines studies ([VAC4EU 2021](#)).

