### Inclusion Criteria

#### AZD1222 Matched Cohort

Subjects in the **AZD1222 matched cohort** will include those subjects in the *all vaccinated first dose population* (ie, received at least 1 dose of AZD1222 within the study period, and this was their first COVID-19 vaccine dose) that fulfil *all* the following inclusion criteria:

- Have at least 12 months of data available before the index date
- Have no record of vaccination with any other COVID-19 vaccine on or before the index date

The **index date** will be the date when a subject receives the first AZD1222 dose within the study period.

For the comparison with the active comparator cohort, only AZD1222 vaccinees with a first and second dose of AZD1222 will be selected. The **index date** for this comparison will be the date of the second dose.

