### Historical Comparators Cohort

A potential comparator subject (**historical comparators**) identified during the period between 2017 and 2018 will be eligible to be matched from the date the subject met all the following inclusion criteria:

- Had at least 12 months of prior data available.

The **index date** for the historical comparators will be same day and month of the AZD1222 index date minus 3 years (subjects from 2018) or 4 years (subjects from 2017)—an approach that intends to address seasonality.

Subjects will be **matched** to AZD1222-vaccinated subjects on age ( $\pm 2$  years), sex, region, and status according to the 5 special populations. Matching will be done with replacement at a ratio of 1:1.

Whether all potential comparators, or only a sample, will be included in the selection of the comparator cohorts will depend on the data governance rules and data management capabilities of each research partner, which is still to be determined. The SAP will document this decision, along with other details about matching criteria.

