Indicators of other relevant comorbidities (diagnosis and procedure codes as applicable)
Chronic obstructive pulmonary disease
Diabetes mellitus
Chronic neurological disease (eg, Parkinson's disease, motor neuron disease, cerebrovascular disease)

Metastatic cancer
Heart failure
Peripheral vascular disease
Chronic liver disease
Substance use disorders
Chronic pancreatic diseases
Chronic kidney disease
Peritoneal dialysis or haemodialysis
To identify subjects who received vaccines to prevent diseases other than COVID-19 recently before cohort entry
Pneumococcal vaccine
Influenza vaccine
Shingles (H. Zoster) vaccine
Other routine scheduled vaccinations
To explore potential dose effect
AZD1222 dose number
To explore effects by age group
Age will be categorised as age categories in line with published background incidence rates from ACCESS (0-19, 20-29, 30-39, 40-49, 50-59, 60-69, 70-79, and greater than 80 years) although this may be collapsed if needed

a Missing information as per the most current approved EU RMP at the time of protocol approval.

Note: A final list of covariates and their operational definitions will be specified in the SAP.

ACCESS, vACcine Covid-19 monitoring readinESS; COVID-19, coronavirus disease 2019; EU, European Union; GBS, Guillain-Barré syndrome; RMP, risk management plans; SAP, statistical analysis plan.

**Annex Table 3 Covariates Proposed to Define Baseline Characteristics and to Be Considered in Estimation of the Propensity Score**

Sociodemographic and lifestyle
Age (in years)
Sex
Month/year at index date
Ethnicity and/or race
Geographic region
Socioeconomic status (employment/occupational status, income, education, index of multiple deprivation)
Healthcare or essential worker status
Residence in long-term facility or nursing home
Smoking or use of smoking cessation drugs
Body mass index (BMI) > 30, obesity diagnosis or obesity surgery
History of alcohol abuse/dependence or alcohol-related diseases
Duration of available health history before cohort entry
Calculated as index date minus earliest date of data availability
Healthcare resource utilisation (look-back period for each variable to be specified in the SAP)
Number of hospitalisations
Number of hospitalisations requiring intensive care
Number of emergency department visits
Any stay in a skilled nursing facility or nursing home
Number of outpatient specialist visits

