Number of outpatient primary care visits
Number of prescriptions/dispensing for any drug
Receipt of influenza vaccine in prior 12 months
Cancer screening tests (eg, mammography, colonoscopy) in prior 12 months, as indicated
Diagnostic testing for COVID-19
COVID-19 history
Previous COVID-19 diagnosis
Positive test result for COVID-19
Other vaccination history
Recent pneumococcal vaccine
Recent influenza vaccine
Recent shingles vaccine
Recent other scheduled vaccines

Indicators of pregnancy or breastfeeding
Pregnancy status at cohort entry
Breastfeeding status at cohort entry (as available)
Indicators of immunosuppression
Organ transplant recipient
Specific haematological neoplasias
Human immunodeficiency virus (HIV) infection
Other congenital or acquired immunodeficiencies or immunosuppressive diseases
Recent or current use of immunosuppressive medications (eg, cytotoxic chemotherapy, biologic immunomodulatory therapies, azathioprine, methotrexate, chronic corticosteroid use)
Indicators of frailty
Dispensing of or reimbursement for durable medical equipment (eg, wheelchairs, home oxygen)
Residence in long-term facility or nursing home
History of hip fracture
Palliative care
Metastatic cancer
Cachexia
Dementia
Pressure ulcers
Bladder incontinence
Indicators of autoimmune or inflammatory disorders
Rheumatoid arthritis
Polymyalgia rheumatica
Psoriasis
Psoriatic arthritis
Vasculitis (any)
Spondylarthritis (any)
Systemic lupus erythematosus
Inflammatory bowel disease (ulcerative colitis and Crohn's disease)
Potential indicators of anaphylaxis risk
History of anaphylaxis
Drug allergies
Food/latex/insect bite allergies
Atopic dermatitis
Epinephrine auto-injector prescription or redemption

Other comorbidities
History of allergies not elsewhere mentioned
Diabetes mellitus (types 1 and 2)
Diabetic complications (renal, ophthalmic, neurologic, amputations and other)
Hypertension
Heart failure
Peripheral vascular disease
Hyperlipidaemia
Ischaemic heart disease
Supraventricular tachyarrhythmias including atrial fibrillation
History of ventricular tachycardia or fibrillation
Receipt of internal cardiac defibrillator
Cardiac conduction system disorder/pacemaker insertion
Valvular heart disease
Peripheral vascular disease
Cerebrovascular disease
Chronic neurological diseases (eg, Parkinson's disease, motor neuron disease, epilepsy)

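### In the exploratory AZD1222–historical comparison, the open-ended look-back can give vaccinees up to 3–4 more years of recorded diagnoses than their comparators

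*Protocol*

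**What the plan says.** - **Look-back.** Section 9.3.3 states that "The look-back observation period to define covariates of interest will be all available information before the index date in each data source". The sentence goes on to allow a different window where one is specified. Medical conditions are taken "at any time before or on the index date, unless otherwise specified", and absence of a code or proxy is read as absence of the condition. Comedication and healthcare use have a 183-day default window (Section 9.3.3 and the note to Figure 6).
- **Historical index date.** Section 9.2.1.1.3 sets it at the "same day and month of the AZD1222 index date minus 3 years (subjects from 2018) or 4 years (subjects from 2017").
- **Minimum history.** For historical comparators: "Had at least 12 months of prior data available". For the AZD1222 matched cohort: "Have at least 12 months of data available before the index date". Both are floors, and neither cohort has a cap.
- **Matching.** Historical comparators are matched on age, sex, region and status in the 5 special populations. Prior COVID-19 is dropped for this comparison.
- **Propensity score.** Section 9.7.3.2 fits a separate logistic model for each of the three comparisons. Candidates for all three come from Appendix C, Annex Table 3, which includes "Month/year at index date", duration of history ("Calculated as index date minus earliest date of data availability"), prior COVID-19 diagnosis, positive COVID-19 test and "Diagnostic testing for COVID-19".
- **Status of the comparison.** It is exploratory objective 2 (Section 8). Historical comparators were added because concurrent unvaccinated follow-up was too short for AESIs with 180- or 365-day windows (Sections 9.1.1 and 9.9.1).

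**The concern.** An open-ended look-back treats both cohorts alike when their index dates fall at the same calendar time. Here one cohort is indexed years earlier in the same databases, so the rule stops being symmetric. The protocol names no exception for this comparison.

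A diagnosis old enough to lie in the vaccinee's extra years is counted for the vaccinee. The equivalent record would be invisible for the comparator, who would be coded as free of the condition. Comparators classed as condition-free then include more people who have the condition than vaccinees classed the same way. If the condition raises AESI risk, the comparator rate is too high within that class and the IRR or HR tends downwards. In a safety study that is the direction that hides a signal.

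The planned diagnostics would not show this. Matching and the standardised differences of Section 9.7.3.3 work on recorded status, so recorded balance can look good while true status differs.

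The stake is larger than the exploratory label suggests. Concurrent follow-up is short, and the active-comparator analysis may be reconsidered after the feasibility assessment (Section 9.7.3.4). The historical comparison could then carry much of the evidence on long-window AESIs.

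**Working it through.** **The plan's own figure.** The only numerical claim for this comparison is in Section 9.5: a 96% probability that the upper limit is below 3.0 for Guillain-Barré syndrome. Expected events per cohort are 5,000,000 × 84/365.25 × 2/100,000 = 23.0. Then Φ(ln 3/√(1/23.0 + 1/23.0) − 1.96) = 0.961, so the figure reproduces. It does not depend on look-back, and nothing below changes it.

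**Step 1: the gap in years.** Take the same registration start s for both members of a pair. Vaccinee history is (index − s). Comparator history is (index − 3 or 4 years − s). The difference is exactly 3 or 4 years for continuously registered people. A later common calendar start for data extraction does not remove it. Turnover shrinks it: simulating assumed turnover of 5–20% per year and an assumed data start of 2005–2015 gives a mean gap of about 0.2–3.4 years.

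**Step 2: which variables are affected.**

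| Affected | Not affected |
|---|---|
| Frailty/comorbidity stratum | Pregnancy/breastfeeding (status at entry) |
| Autoimmune/inflammatory stratum | Recent other vaccines |
| Diagnosis-based part of immunocompromised stratum | Medication and healthcare use (183 days) |
| Diagnosis-history propensity-score covariates | AESI clean intervals (Table 3) |

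**Step 3: illustrative size.** Section 9.4.2 dates high coverage of VID ambulatory records from 2009. That gives about 2021 − 2009 = 12 years for vaccinees, and 2018 − 2009 = 9 or 2017 − 2009 = 8 years for comparators. The first-recording rate λ is an assumption. In two identical populations, recorded prevalence is p = 1 − exp(−λT), and the standardised difference is (p₁ − p₀)/√{[p₁(1 − p₁) + p₀(1 − p₀)]/2}.

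| λ per year (assumed) | p, 12 years | p, 9 years | p, 8 years | Standardised difference (12 v 9; 12 v 8) |
|---|---|---|---|---|
| 1% | 11.3% | 8.6% | 7.7% | 0.09; 0.12 |
| 2% | 21.3% | 16.5% | 14.8% | 0.12; 0.17 |
| 3% | 30.2% | 23.7% | 21.3% | 0.15; 0.20 |

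Over wider assumptions (0.5–2% per year, 1–15 years of comparator history, the full 3- or 4-year gap), the range is 0.05–0.33. These are differences in recorded status before adjustment. They are not estimates of bias in the IRR or HR.

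**Step 4: the propensity-score candidates.** Historical index dates lie in 2017–2018 and the matched AZD1222 dates 3 or 4 years later.

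- Month/year at index date: AUC 1.00. A logistic fit on simulated dates failed with a singular matrix, which is complete separation.
- Month alone: AUC 0.50, because day and month are aligned by design.
- A COVID-19 item: always zero in comparators. With share p positive among vaccinees, AUC = 0.5 + p/2, or 0.51–0.60 for assumed p of 2–20%. A positive value identifies a vaccinee, but a zero identifies nobody, so separation is one-sided.
- Duration of history: shifted by design, but the distributions can overlap.

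**The case against.** Several points on the other side are sound.

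- **The protocol leaves room.** Section 9.3.3 allows alternative look-backs, and the final covariate list and definitions are left to the SAP. An equal window could be set there without contradicting the protocol. This stands. But the default is fixed in the protocol, no exception is stated for this comparison, and following it as written produces the asymmetry.
- **Annex Table 3 is only a candidate list.** Section 9.7.3.1 also excludes covariates that affect treatment alone. A reader might infer that the historical propensity-score model must break down. The documents do not support that, because nothing obliges calendar year or the COVID-19 items to enter. Equally, the exclusion rule would not clearly remove them: Sections 9.1.1 and 9.9.1 say background AESI rates may have changed during the pandemic, so these items may relate to outcomes as well.
- **The scope is limited.** A reader might infer that every vaccinee has 3–4 extra years, or that all five special populations are distorted. Neither follows. The gap is a maximum, and two of the five populations are unaffected.
- **The illustration is partial.** It uses one of five data sources and treats 2009 as the data start, whereas Section 9.6.1 leaves the extraction period to the ETL instructions. It also assumes that ascertainment grows only with cumulative first recording. Chronic conditions re-recorded at routine contacts would be found in a shorter window, which would narrow the difference.
- **The protocol already flags non-comparability of historical comparators.** It does so for pandemic effects and healthcare access, not for length of look-back.

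**Conclusion.** The point holds as an asymmetry in covariate ascertainment, confined to diagnosis-history variables in one exploratory comparison. The extra history is up to 3–4 years for continuously registered vaccinees and less with turnover. The likely direction is towards a lower IRR or HR for conditions that raise AESI risk. The size of that effect cannot be derived from the documents. The standardised differences of 0.09–0.20 rest on a 2009 data start in VID and assumed recording rates of 1–3% per year.

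The propensity-score point is secondary: calendar year would separate the cohorts completely if used, and the COVID-19 items would do so in one direction only.

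A reader might also infer that the primary results are compromised. They are not: primary objective 4 uses concurrent unvaccinated comparators and the self-controlled design, where this calendar gap does not arise.

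**What to change.** For the AZD1222–historical comparison only:

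1. Define diagnosis-based special-population status and diagnosis-history propensity-score covariates over a look-back of equal length in both cohorts. Alternatively, truncate the vaccinee's history to the matched comparator's length. For the matching strata a fixed window is simpler, because status is needed before the pair exists. The current floor guarantees only 12 months for everyone, so a longer fixed window would need a higher history requirement in both cohorts.
2. State that this propensity score uses month at index without calendar year and omits COVID-19 diagnosis, positive test and testing. Duration of history becomes unnecessary once look-backs are equal.

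The cost is a few sentences in Section 9.3.3 and Annex Table 3 or the SAP, plus one extra covariate derivation that feeds the historical matching. Some older diagnoses are dropped for vaccinees in this comparison. No study-size figure changes unless a higher history requirement reduces the matched numbers.

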**Table 3 Adverse Events of Special Interest and Other Safety Concerns**

Adverse event	Suitable for SCRI analysis according to ACCESS protocol template a	Risk interval after index date (days)	Clean look-back interval (days) k
Vaccine-associated enhanced disease, including vaccine-associated enhanced respiratory disease, including ARDS	No	14-365 b	365
Multisystem inflammatory syndrome in adults/children	Yes	1-42 c	365 c
Sudden death	No	0-6 b	Not applicable
Autoimmune thyroiditis	No d	1-180 e	365
Anosmia, ageusia	No f	1-365 e	365
Anaphylaxis	Yes	0-2 c	180 c

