**Figure 6 Summary of Covariate Ascertainment in Cohort Analyses**

a Earliest end date of study period, enrolment termination date, death, vaccination with any COVID-19 vaccine other than the vaccine granting access to the cohort, also for each specific AESI: date of the AESI, end of risk window for that specific AESI.

Note that information on inclusion, exclusion, and covariate assessment windows will all be available before the index date in each data source, except when an alternative look-back-specific risk window is specified. For comedications and healthcare utilisation, this time window will be 183 days before the index date, except if a different time window is specified for specific medications or healthcare utilisation measures.

AESI, adverse event of special interest; COVID-19, coronavirus disease 2019.

Source: Original design diagram template can be found at [www.repeatinitiative.org/projects.html](http://www.repeatinitiative.org/projects.html).

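### Condition and medication look-backs include the vaccination day, so an anaphylaxis on the day of the index dose can enter the propensity score as history and also count as the outcome

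*Protocol*

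**What the plan says.** **Covariate windows (section 9.3.3).** Conditions are taken from records "at any time before or on the index date, unless otherwise specified". Medications are taken from records "in the 183 days before or on the index date, unless otherwise specified". The general sentence earlier in the same section sets the look-back as "all available information before the index date in each data source, except when an alternative look-back window is specified". The Figure 6 note says: "For comedications and healthcare utilisation, this time window will be 183 days before the index date", with exceptions allowed.

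**Index date (section 9.2.1.1.3).** For the AZD1222 matched cohort it "will be the date when a subject receives the first AZD1222 dose within the study period". Day 0 is therefore the exposure day. The two-dose comparison with mRNA vaccinees uses the second-dose date instead.

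**Outcome windows (Table 3).** The anaphylaxis row reads "Anaphylaxis Yes 0-2". Sudden death has days 0-6 and generalised convulsions days 0-14. Nearly all other events start on day 1 or later.

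**Covariates (Appendix C, Annex Table 3).** The candidates include "History of anaphylaxis", drug allergies, epinephrine auto-injector, antihistamines, and epilepsy as an example of chronic neurological disease. Section 9.7.3.1 proposes one propensity score per comparison for all outcomes.

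**Prior-event exclusion (section 9.2.1.1.3).** It looks only before the index date.

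**The concern.** A baseline covariate should be fixed before exposure can act on it. Under the section 9.3.3 default, a person whose first anaphylaxis follows the dose on the same day has a qualifying diagnosis on the index date, and possibly a qualifying prescription. That record meets the definition of baseline history. The same event falls inside the day 0-2 window and is the outcome. The prior-event exclusion does not remove the person, because it stops before the index date, and no rule says which definition takes precedence.

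The case is then weighted, stratified or matched as if the person belonged to the small group with a true history. How far this moves the estimate depends on how that group was distributed between AZD1222 and the comparator. Anaphylaxis is a safety concern in the risk management plan (section 7), and few cases are expected, so a few misplaced cases can matter.

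**Working it through.** **1. Does the protocol count day 0 as outcome time?** The notes to Tables 5 and 6 give anaphylaxis 3 days × 2 doses = 6 days. The check uses the precision formula P = Φ(ln U / SE − 1.96), with SE = √(1/a + 1/b) and a = N × days/365.25 × 6/100,000. For Table 5, b = a/3 (the 3:1 person-time in its title).

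For N = 5,000,000 and 6 days, a = 4.93.

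| U | 1.5 | 2.0 | 2.5 | 3.0 |
|---|---|---|---|---|
| Table 5 | 0.07 | 0.12 | 0.17 | 0.23 |
| 6 days (day 0 counted) | 0.066 | 0.117 | 0.173 | 0.229 |
| 4 days (day 0 dropped) | 0.056 | 0.091 | 0.129 | 0.167 |

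All anaphylaxis cells of Tables 5 and 6 reproduce with 6 days; with 4 days the tables do not. Day 0 is outcome time in the protocol's own arithmetic, and section 9.3.3 makes the index day covariate time as well. No planning figure is in dispute.

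**2. Which outcomes and analyses are reached?**
- Anaphylaxis: directly, because its history is itself a listed covariate.
- Generalised convulsions: only through an epilepsy code on the same day.
- Sudden death: only through same-day codes for related conditions, such as ventricular fibrillation.
- Day 0 of dose 2 in the unvaccinated and historical comparisons: not reached, because the covariate window closed at dose 1. For a two-dose recipient the overlap is 1 of 6 at-risk days for anaphylaxis.
- Two-dose comparison with mRNA vaccinees: the index date is dose 2 and both arms are vaccinated on it, so same-day coding can arise in both.
- Crude estimates and the self-controlled analysis: not reached, because neither uses a propensity score.

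**3. Illustration of size (assumed inputs).** One binary covariate, inverse probability weighting, equal cohorts, and a true ratio of 3 (15 vs 5 cases). Recorded history is 0.2% in vaccinees and 0.4% in comparators.
- Score in the history stratum: 0.2/(0.2 + 0.4) = 1/3. Weights are 3 for vaccinees and 1.5 for comparators; outside the stratum they are about 2.
- Correct coding: (15 × 2)/(5 × 2) = 3.0.
- All vaccinee cases on day 0 of dose 1, one third of comparator cases on day 0: mean comparator weight (1/3)(1.5) + (2/3)(2) = 1.83. Ratio (15 × 3)/(5 × 1.83) = 4.9.
- Imbalance reversed: mean comparator weight (1/3)(3) + (2/3)(2) = 2.33. Ratio (15 × 1.5)/(5 × 2.33) = 1.9.
- Half of vaccinee cases after dose 2, one sixth of comparator cases on the index date: (7.5 × 3 + 7.5 × 2)/(5 × [(1/6)(1.5) + (5/6)(2)]) = 37.5/9.58 = 3.9.
- The same, reversed: (7.5 × 1.5 + 7.5 × 2)/(5 × [(1/6)(3) + (5/6)(2)]) = 26.25/10.83 = 2.4.

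**4. When it is negligible.** This second illustration covers the dose-1 window only: 1 million per cohort, 6 per 100,000 person-years, and one excess day-0 case. Background is 0.164 cases per day, so the true ratio is (0.493 + 1)/0.493 = 3.03.

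| True history, vaccinees / comparators | Ratio with day-0 events coded as history |
|---|---|
| 0.2% / 0.2% | 3.03 |
| 0.002% / 0.002% | 2.95 |
| 0.1% / 0.2% | 4.59 |
| 0.2% / 0.1% | 2.09 |

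**The case against.** **The SAP may settle it.** Section 9.3.3 allows other windows, Annex Table 3 lists only candidates, and operational definitions are left to the SAP. That is fair, but the protocol does state a default, and the default is unsafe for an outcome counted from day 0. Permission to depart from it does not correct it. The Figure 6 diagram, which is not in the available text, might also clarify day 0; its note does not.

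**The contradiction is limited.** The general look-back sentence gives way to a specified alternative, and section 9.3.3 specifies one for conditions. The real tension is over medications, where section 9.3.3 includes the index date and the Figure 6 note does not mention it.

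**Stronger readings that a reader might infer.** The documents do not support these:
- That emergency visits and hospitalisations on day 0 become baseline covariates. The inclusive wording covers conditions and medications only. Healthcare use falls under the Figure 6 note, and Annex Table 3 leaves its look-back to the SAP.
- That every day-0 case of all three outcomes is coded as its own history. Only anaphylaxis duplicates a listed covariate. The auto-injector item is a prescription or redemption, not acute treatment.
- That 4.9 or 1.9 is the expected distortion. Those figures need every vaccinee case on day 0 of dose 1, a two-fold imbalance, a single covariate and weighting. Section 9.7.7 leaves matching, stratification or weighting to the SAP.

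**Conclusion.** The point holds in narrow form. Followed as written, section 9.3.3 lets an anaphylaxis on the day of the index dose act as both baseline history and outcome in the propensity-adjusted cohort analyses. Convulsions and sudden death are exposed only through related same-day codes.

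The documents do not give the size or direction of the bias. It is negligible when true history is balanced and common relative to cases. With an assumed two-fold imbalance, a true ratio of 3 moves to about 3.9 or 2.4 if half of vaccinee cases follow dose 2. The outer values of 4.9 and 1.9 need all of them on day 0 of dose 1. The prevalences, the timing split, the single covariate and the weighting are all assumptions. The crude and self-controlled estimates offer a partial cross-check for anaphylaxis. The correction is cheap enough to be worth making.

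**What to change.** In section 9.3.3, end the look-back for diagnosis-based and medication-based propensity-score covariates on the day before the index date. At a minimum, do this for covariates that can be a manifestation or treatment of an event whose Table 3 window starts on day 0. Reconcile the medication wording of section 9.3.3 with its general look-back sentence and with the Figure 6 note.

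Leave unchanged any status that Appendix C defines at cohort entry (pregnancy, breastfeeding), and keep vaccines co-administered on the index date. Shifting every special-population look-back could drop those vaccines, although interaction with other vaccines is listed as missing information in section 7.

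The cost is one sentence in the protocol and a one-day shift in the extraction code. The downside is that true history first coded at the vaccination visit is lost. No sample-size or precision figure changes.
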